Visit 4: End of Treatment (Days 14 & 15 ±1 day): Patients will attend the CPU with their BronkoTest[®] diary card and study medication on the morning of Day 14 in fasted state, having fasted from midnight (water will be allowed for thirst up until 1 hour before dosing) and having withheld taking their morning dose of study medication, and stay until the morning of Day 15. Blood will also be collected pre-dose for assessment of PK, hsCRP and serum amyloid A. Before administration of the morning dose on Day 14, safety assessments (vital signs, ECG, lung function, haematology, clinical chemistry, urinalysis and urine drug screen) will be performed. Patients will then take their morning dose of study medication in the CPU. This will be the final dose of study medication. At 1 hour post-dose, an ECG will be recorded. Approximately 1-2 hours after this last dose, patients will provide an induced sputum sample (around the same time they had the induced sample on Day -1); weight of the sample will be recorded, and the sample processed for neutrophils and AZD9668 levels.

All urine produced over the 24 hours after the last dose will be collected for measurement of desmosine levels and AZD9668 concentrations. Urine will be collected for time periods 0-4 hours, 4-12 hours and 12-24 hours. Aliquots from each of these collections will be taken for urine PK, and an aliquot from the pooled sample will be taken for urine desmosine. Serial blood samples will be collected for PK analysis at pre-dose and at 0.25, 0.5, 1, 2, 3, 4, 5, 6, 8, 12, and 24 hours post dose. On the morning of Day 15, a spontaneous sputum sample will be collected for quantitative bacteriology, and the patients will be discharged from the CPU with their BronkoTest[®] diary card to bring to their follow-up visit.

Visit 5: Follow-up (Day 21 ±3 days): Patients will return to the CPU with their BronkoTest[®] diary card in fasted state, having fasted from midnight (water allowed), for follow-up safety assessments (physical examination, vital signs, ECG, lung function, haematology, clinical

chemistry and urinalysis). A blood sample for hsCRP and serum amyloid A will also be collected at this visit.

Throughout the study, lung function measurements should be performed at the same time of day ± 2 hours in relation to the time point at Visit 1 (baseline).

Each patient will attend the visits as outlined in Figure 1.

[figure not shown]

Table 1Study plan

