- ^f Urine for desmosine will be collected during the following periods: 24 h period before the first dose (Days -1 to 1) and 24 h period after the last dose (Days 14-15). For the latter, when it coincides with the urine PK, the timed PK samples will be pooled to take an aliquot for urine desmosine.
- ^g For urine PK aliquots will be taken from samples collected for the following periods: 0-4 hours, 4-12 hours and 12-24 hours. On Day -1 only, an aliquot will be taken from the 24-hour collection for the pre-dose sample.
- ^h Serial PK plasma samples to be taken pre-dose and 0.25, 0.5, 1, 2, 3, 4, 5, 6, 8, 12, and 24 hours after the first and last dose (i.e. on Days 1-2 and 14-15). NB the sample taken at 24 hours on Day 2 will be taken pre-dose.
- ⁱ Plasma PK sample taken pre-dose
- ^j BronkoTest[©] diary card to be completed daily by patient throughout the entire study period.
- ^k If consent is not obtained at Visit 1, it can be obtained at any of the subsequent visits. Sampling is planned for the randomisation visit, but can be taken at a subsequent visit

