3.2 Rationale and risk/benefit assessment

3.2.1 Rationale for study design, doses and control groups

Patients with COPD are the target population for the NE inhibitor AZD9668. The main purpose of this study is to establish the tolerability of AZD9668 in patients with COPD as a preliminary to long-term proof-of-concept studies in this population. It is also intended to get pharmacokinetic (PK) data in this population that would help in the planning of future patient studies. So far safety/tolerability and PK data are available in healthy volunteers up to 150 mg as a single dose and up to 120 mg daily for 8 days as multiple doses. A 14-day study in 12

patients with COPD on active treatment is deemed sufficient to establish tolerability in a patient population, before proceeding to longer-term studies in patients with COPD.

The first-in- man, two-part, single and multiple ascending dose (SAD and MAD) study of AZD9668 in healthy volunteers (D0520C00001) is now complete and the reporting phase is underway. In the SAD part of the study the doses that have been safely administered were 2, 10, 30, 60, 120 and 150 mg. Dose escalation was stopped because the exposure limits set by the internal AstraZeneca Human Exposure Limits Committee (HELC) were reached. These limits (i.e. $AUC_{(0-24h)}$ and C_{max} of 18 µM.h and 2.5 µM, respectively) were set following a review of the data obtained in the 1-month toxicology studies in the rat and dog and have been based upon the exposures at the no observed adverse effect level (NOAEL) in rat (370 mg/kg), corrected for the differences in plasma protein binding between the species. The NOAEL in the rat has been used because the free exposures at this dose are lower than those obtained in the dog at the no observed effect level (NOEL) dose. In the MAD part of the study the doses that have been safely administered were 30, 70 and 120 mg once a day for a total of 8 days.

Following single dose administration of AZD9668 (2 - 150 mg) absorption was rapid, median t_{max} ranged from 1h to 2h. The geometric mean CL/F ranged from 15.4 to 21.6 L/h and the geometric mean V_z /F ranged from 157 to 334L. The geometric mean terminal half-life of AZD9668 ranged from 5.04 to 14.99h. The CL/F, V_z /F and $t_{1/2}$ appeared to be independent of dose. The exposure (C_{max} and AUC) increased proportionally with dose between doses of 10mg and 150mg.

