AZD9668 is renally eliminated and renal clearance (CL_R) and the percentage of the dose excreted as unchanged AZD9668 in the urine over 48 h ($F_{e(0-48)}$ (%)) appeared to be independent of dose. The geometric mean CL_R ranged from 5.83 L/h to 6.98 L/h, and the range of the geometric mean $F_{e(0-48)}$ (%) was 31.6 % to 40.0 %.

Following multiple dose administration of AZD9668 (30 mg, 70 mg and 120 mg, once a day for 8 days), absorption was similar following single and multiple dosing; the median t_{max} and $t_{max,ss}$ was 1h for all dose groups. The geometric mean CL/F_{,ss} was 14.7, 14.8 and 19.4 L/h and the geometric mean Vz/F_{,ss} was 191L, 218 and 245L, respectively. The geometric mean $t1/2_{,ss}$ was 9.04h, 10.24h and 8.73h, respectively, and there was no evidence for time or dose dependent change in PK. There was no evidence of accumulation upon multiple dosing to steady state.

AZD9668 is renally eliminated and renal clearance at steady state ($CL_{R,ss}$) and the percentage of the dose excreted as unchanged AZD9668 in the urine at steady state over 48 h ($F_{e(0-48),ss}$ (% dose)) appeared to be independent of dose. The geometric mean $CL_{R,ss}$ was 5.29 L/h, 5.70 L/h and 5.83 L/h, and the geometric mean $F_{e(0-48),ss}$ (% dose) was 38.8 %, 40.9 % and 31.6 %, respectively.

Administration of AZD9668 after consumption of a high fat meal resulted in a reduction in the rate of absorption (median t_{max} was 4 h, 3 h and 4 h for 30 mg, 70 mg and 120 mg, respectively). The C_{max} was reduced by 22 %, 31 % and 22 % and the AUC_(0-24h) was slightly

reduced, by 8 %, 5 % and 5% for 30 mg, 70 mg and 120 mg, respectively. Thus consumption of the food reduced the rate but had relatively little effect on the overall extent of absorption.

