6.4.2 Pharmacokinetic concentrations and variables

The pharmacokinetic analyses will be performed by or under the guidance of International GmbH.

For descriptive statistics of plasma concentrations

- if, at a given time point, 50% or less of the plasma concentrations are nonquantifiable (NQ), the geometric mean (gmean), CV, geometric mean ± SD, arithmetic mean and SD will be calculated by substituting the lower limit of quantification (LLOQ) for values which are NQ.
- if more than 50%, but not all, of the concentrations are NQ, the gmean, CV, gmean ± SD, arithmetic mean and SD will be reported as not calculable (NC)
- if all the concentrations are NQ, the geometric mean and arithmetic mean will be reported as NQ and the CV, gmean ± SD and SD as NC

If the calculation of the geometric mean - SD results in a value less than the LLOQ, NQ will be displayed.

Pharmacokinetic parameters will be calculated using non-compartmental analysis. Plasma concentrations of AZD9668 below the LLOQ at the end of the curve will not be considered for pharmacokinetic analysis, however if concentrations below the LLOQ between measurable concentrations should be set to LLOQ/2. All pre-dose samples which are below LLOQ will be set to zero. The actual sampling time will be used for the analysis. The maximum plasma concentration (C_{max}) and the time to reach the maximum plasma concentration (t_{max}) will be determined by visual inspection of the plasma concentration-time profile. The area under the plasma concentration-time curve from time zero to 24 h after dosing AUC(0-24) and from zero to the time of the last quantifiable plasma concentration (t_{last}) AUC_(0-t), will be calculated using the linear trapezoidal rule (linear/log interpolation). The rate constant of the slowest disposition phase (λ_z) will be calculated by log-linear regression of the terminal portion of the concentration-time profile where there were sufficient data (i.e. at least 3 time points and R^2 adjusted is greater than or equal to 0.9). If these criteria are not fulfilled, AUC, CL/F, $t_{1/2}$ and Vz/F will not be reported. The terminal half-life ($t^{1/2}$) will be derived from the equation $\ln(2)/2$ λ_z . The area under the plasma concentration-time curve from time zero to infinity (AUC) will be determined by using λ_z to extrapolate AUC_(0-t) to infinity (provided less than or equal to

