20% of the AUC is extrapolated). Total apparent drug clearance (CL/F) and the terminal volume of distribution (V_z /F) will be estimated by dividing the dose by AUC, and product of λ_z and AUC, respectively. The equivalent PK parameters determined at steady state will also be calculated.

All pharmacokinetic parameters (except t_{max}) will be summarised by the number of observations, geometric mean, coefficient of variation (CV, calculated as 100 x v [exp (s²)-1], where s is the standard deviation of the data on a log scale), arithmetic mean, standard deviation (SD) using untransformed data, median, minimum and maximum. t_{max} will be summarised using median, minimum and maximum and number of observations.

For the urine data the amount of drug recovered for each individual collection period and the total amount over the collection period will be calculated. In addition the percentage of drug recovered for each collection period (and the total percentage recovered over the collection period) and the overall CL_R will be calculated. Summary statistics will be the same as for the plasma PK parameters.

Plasma concentration profiles will be presented graphically as individual curves and geometric mean plots, by study day, on both linear and log concentration scales.

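### Withholding AUC to infinity when more than 20% is extrapolated, with sampling that ends at 24 h, can remove long-half-life patients selectively from AUC, CL/F and Vz/F

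*Protocol*

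**What the plan says.** Section 6.4.2 extrapolates AUC to infinity from the terminal slope, on condition that no more than "20% of the AUC is extrapolated". In the same section CL/F "will be estimated by dividing the dose by AUC", and Vz/F is the dose divided by the product of the terminal rate constant and AUC. Both are lost when that AUC is not determined. A separate criterion (at least three points, adjusted R² of at least 0.9) governs the terminal slope; failing it removes AUC, CL/F, half-life and Vz/F together. The 20% limit does not remove half-life.

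For both the Day 1 and the Day 14 profile, the study plan notes in section 3.1 read "Serial PK plasma samples to be taken pre-dose and 0.25, 0.5, 1, 2, 3, 4, 5, 6, 8, 12, and 24 hours". Section 6.4.1 rules out imputation. The synopsis lists AUC, CL/F and Vz/F, with their steady-state counterparts, among the primary PK variables.

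Section 3.2.1 gives the volunteer data. After single doses the "geometric mean terminal half-life of AZD9668 ranged from 5.04 to 14.99h". On multiple once-daily dosing at 30, 70 and 120 mg, the geometric mean half-life "was 9.04h, 10.24h and 8.73h, respectively".

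**The concern.** A 20% limit guards against unreliable extrapolation and does little harm when sampling covers several half-lives. Here the window is only two to three of the stated typical half-lives, so the limit can fall within the expected spread of patients.

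Whether a value is kept then depends on the patient's half-life, which is fixed by Vz/F and CL/F, two of the quantities being summarised. The retained patients would show CL/F too high, and AUC to infinity and Vz/F too low. Plasma PK in COPD is a primary objective, the study is descriptive so the summary is itself the result, and section 3.2.1 says the data should help plan later patient studies. The summaries would also fail to reconcile: half-life would include patients missing from CL/F and Vz/F.

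**Working it through.** **Consistency of the stated inputs.** Half-life = ln 2 × (Vz/F)/(CL/F), using the multiple-dose values in section 3.2.1:

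- 30 mg: 0.693 × 191/14.7 = 9.01 h (stated 9.04)
- 70 mg: 0.693 × 218/14.8 = 10.21 h (stated 10.24)
- 120 mg: 0.693 × 245/19.4 = 8.75 h (stated 8.73)

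The figures agree.

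**Where the limit bites on Day 1.** Let w be the share of single-dose AUC carried by the terminal phase (w = 1 is mono-exponential). The share beyond 24 h is f = w × exp(−24 × ln 2/t½). Setting f = 0.20 gives t½ = 24 × ln 2/ln(w/0.2):

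- w = 1.0: 16.64/ln 5 = 10.3 h
- w = 0.8: 16.64/ln 4 = 12.0 h
- w = 0.6: 16.64/ln 3 = 15.1 h

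With w = 1, f is 14.9% at 8.73 h, 15.9% at 9.04 h, 19.7% at 10.24 h and 33.0% at 14.99 h.

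**Which w is plausible.** Two statements in section 3.2.1 point below 1.

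- No accumulation was evident on once-daily dosing. At 9.04 h the expected AUC ratio is 1/(1 − 0.159) = 1.19 for w = 1 and 1/(1 − 0.6 × 0.159) = 1.10 for w = 0.6.
- The Cmax,ss margin of 2.6 against a limit of 2.5 µM implies 2.5/2.6 = 0.96 µM. With 60 mg = 60/545.5 × 1000 = 110 µmol, the one-compartment upper bound (110/Vz)/(1 − exp(−12 × CL/Vz)) is 0.955, 0.905 and 0.732 µM for the three groups, all below 0.96.

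**Loss and bias.** Assumptions not in the protocol: log-normal, independent CL/F and Vz/F, each with CV 20–40%. With s = √ln(1 + CV²), z = ln[(CL/Vz) ÷ (ln(w/0.2)/24)]/(s√2), φ the standard normal density and Φ its distribution function, the share lost is 1 − Φ(z). Geometric mean CL/F is multiplied by exp[(s/√2) × φ(z)/Φ(z)]; AUC to infinity and Vz/F are divided by the same factor.

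Example (30 mg values, w = 0.8, CV 30%): s = 0.294; z = ln(0.0770/0.0578)/0.415 = 0.69; lost = 24%; factor = exp(0.208 × 0.416) = 1.09.

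| Group values | w | Lost of 12 active (CV 20–40%) | CL/F bias |
|---|---|---|---|
| 30 mg | 1.0 | 3.7–4.8 | +7% to +19% |
| 30 mg | 0.8 | 1.8–3.6 | +4% to +14% |
| 30 mg | 0.6 | 0.4–2.0 | +1% to +9% |
| 70 mg | 1.0 | 5.8–5.9 | +11% to +24% |
| 70 mg | 0.8 | 3.4–4.6 | +7% to +18% |
| 70 mg | 0.6 | 1.0–2.8 | +2% to +12% |
| 120 mg | 1.0 | 3.3–4.6 | +7% to +18% |
| 120 mg | 0.8 | 1.6–3.4 | +3% to +14% |
| 120 mg | 0.6 | 0.3–1.9 | +1% to +8% |

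If the 14.99 h single-dose group were typical, losses would be larger; if the 5.04 h group were, f would be under 4% and losses small.

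**Day 14.** Section 6.4.2 says only that equivalent steady-state parameters will be calculated. If the same limit applies to AUC extrapolated after twice-daily dosing, and the fast phase is assumed to have a 1 h half-life, the cut-offs are 11.2 h (w = 0.8) and 12.5 h (w = 0.6), lower than on Day 1.

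**The case against.** The strongest objections concern breadth and size, and most of them stand.

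- **Exposure.** A reader might infer that exposure in general is biased low. The documents do not support that. The limit applies only to AUC to infinity and what is derived from it. Cmax, AUC(0-t), AUC(0-24) and C24 do not depend on it, the human exposure limits in section 3.2.1 use Cmax and AUC(0-24), and Rac uses AUC(0-24).
- **Renal clearance.** CL_R, the clearance named in the primary objective, is not tied to the limit in the text.
- **Who is dropped.** A reader might infer that patients go because clearance is low. Selection is on half-life, so a large Vz/F with ordinary clearance is dropped too.
- **Size.** A reader might infer that a typical patient sits at the cut-off and that up to half are lost. That needs mono-exponential decline, which the accumulation and Cmax,ss statements argue against. Independence also matters: CL/F and Vz/F share 1/F, so positive correlation is plausible. With an assumed correlation of 0.5, CV 30% and w of 0.65–0.80, loss is 5–29% and bias +2% to +7%; at CV 20% and w = 0.65 it is 1–5% and about +0.2% to +1%.
- **Visibility.** The number of observations is reported per parameter and derived data are listed, so losses would be seen, and slow eliminators stay in the half-life summary. That reveals the gap but does not correct the summaries.
- **Reliability.** Only the 12 h and 24 h samples follow 8 h, so heavily extrapolated values are imprecise. This is a sound reason not to make them the sole main summary. It does not require deleting them.

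The study tests no hypothesis, so no decision rule changes.

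**Conclusion.** The point holds for AUC to infinity, CL/F and Vz/F. The stated limit and the 24 h window can produce informative missingness in these three primary PK variables, and the stated half-lives make that plausible. The direction is clear: CL/F up, AUC to infinity and Vz/F down.

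The size is not determined by the protocol, which gives neither between-patient variability nor curve shape. Over the multiple-dose group values, with CVs of 20–40%, w of 0.6–1.0 and independence, the CL/F bias runs from about +1% to +24%. Losses run from under one patient to about five of 12 at the 30 mg values, and nearly six at the 70 mg values with mono-exponential decline. The upper end depends on the assumption the protocol's own figures fit least well, and positive correlation lowers the whole range. Nothing here shows that the protocol's main exposure comparison, on Cmax and AUC(0-24), is compromised.

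**What to change.** In section 6.4.2, replace the deletion with a flag. Calculate and list AUC, CL/F and Vz/F for every patient who meets the existing terminal-slope criteria, and mark values with more than 20% extrapolated. Present the summaries side by side with and without the marked values, and give the number marked. Base the Day 1 exposure statement on AUC(0-24), which is already a planned variable and needs no extrapolation to infinity.

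The cost is one changed sentence and one extra table. The downside is that flagged values carry more extrapolation error, which is why both summaries should be shown.

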6.4.3 Pharmacodynamic measurement and variables

6.4.3.1 Induced sputum weight, neutrophils in sputum and other biomarkers

The ratio of the neutrophils in sputum (and other biomarkers and sputum weight) on active to placebo will be analysed. This will be performed using analysis of variance, modelling the data on a log scale and then back transforming the results, the baseline values will be included as covariates. If the data cannot be transformed then the data will be analysed using a non-parametric test (Wilcoxon rank sum) instead. The medians will be estimated using Hodge-Lehmann procedure.

6.4.4 Safety analysis

Examination of the following safety variables will address the primary objective to investigate the tolerability of 14 days' treatment with AZD9668. No formal hypotheses will be associated with these variables, although informal comparisons will be made between treatment groups to determine whether there appears to be any treatment-related effects: adverse events, vital signs, 12-lead ECG (overall evaluation), lung function, sputum bacteriology, safety lab data (clinical chemistry, haematology, urinalysis), physical examination and concomitant medication.

Adverse events will be analysed by means of descriptive statistics and qualitative analysis. AEs will be listed for each patient and summarised by System Organ Class and preferred term assigned to event by using MedDRA 10.0.

Concomitant medications will be classified according to the AZDD Drug Dictionary, the ATC system and the CPMP route of administration dictionary. All concomitant medications reported at entry and recorded during the study will be summarised and listed.

6.4.5 Secondary outcome and exploratory variables

See Section 6.4.3 Pharmacodynamic measurement and variables

BronkoTest[©] diary card data: PEF, symptom scores and sputum scores (including amount and colour), the markers of tissue degradation, and the inflammatory markers in plasma will be summarised, plotted and listed.

6.5 Determination of sample size

No formal statistical sample size calculation has been performed for this phase II trial. The number of patients included is based on feasibility.

6.6 Interim analyses

No interim analysis will be performed.

6.7 Data monitoring board

Not applicable in this study.

7. STUDY MANAGEMENT

7.1 Monitoring

Before first patient into the study, a representative of AstraZeneca will visit the investigational study site to:

- Determine the adequacy of the facilities
- Discuss with the investigator(s) (and other personnel involved with the study) their responsibilities with regard to protocol adherence, and the responsibilities of AstraZeneca or its representatives. This will be documented in a Clinical Study Agreement between AstraZeneca and the investigator
- Discuss the specific requirements of the genetic research with the investigator(s) (and other personnel involved with the study)

During the study, a monitor from AstraZeneca or company representing AstraZeneca will have regular contacts with the study site, including visits to:

- Provide information and support to the investigator(s)
- Confirm that facilities remain acceptable
- Confirm that the investigational team is adhering to the protocol, that data are being accurately recorded in the eCRFs/pCRFs, and that investigational product accountability checks are being performed

- Perform source data verification (a comparison of the data in the eCRFs/pCRFs with the patient's medical records at the hospital or practice, and other records relevant to the study). This will require direct access to all original records for each patient (eg, clinic charts).
- Perform source verification of the genetic consent of participating patients and ensure that the investigational team is adhering to the specific requirements of this genetic research.

The monitor or another AstraZeneca representative will be available between visits if the investigator(s) or other staff at the centre need information and advice.

7.2 Audits and inspections

Authorised representatives of AstraZeneca, a regulatory authority, an Ethics Committee may visit the centre to perform audits or inspections, including source data verification. The purpose of an AstraZeneca audit or inspection is to systematically and independently examine all study-related activities and documents to determine whether these activities were conducted, and data were recorded, analysed, and accurately reported according to the protocol, Good Clinical Practice (GCP), guidelines of the International Conference on Harmonisation (ICH), and any applicable regulatory requirements. The investigator should contact AstraZeneca immediately if contacted by a regulatory agency about an inspection at his or her centre.

